1.3 Schedule of Assessments

Table 1 Schedule of Assessments

Trial Periods/Phases	Screening Period ^{a,b,c}	Treatment Period										Follow-up ^d	
		-2 to -1	-	1	2	3 ^e	-	4	5	6 ^f	ET ^g		
Week	-2 to -1	-	-	1	2	3 ^e	-	4	5	6 ^f	ET ^g	10	
Day	-15 to -1	1/ Baseline ^h	4	7±2	14±2	21±2	24	28±2	35±2	42±2	45±2	NA	73±3
Entrance and History													
Informed consent	X												
Inclusion/exclusion criteria	X	X ⁱ											
Medical and psychiatric history ^j	←-----→												
MINI	X												
Demography	X												
History of drug and alcohol use	X												
Smoking history	X	X											
Review of birth control methods	X												
Breathalyzer test for alcohol ^k	X												
SARS-CoV-2 testing ^c	X												
Randomization		X											
Efficacy/Health Economics Assessments^l													
PANSS	X	X		X	X	X		X	X	X		X	
CGI-S	X	X		X	X	X		X	X	X		X	
CGI-I ^m						X				X		X	

Trial Periods/Phases	Screening Period ^{a,b,c}	Treatment Period										Follow-up ^d
		-2 to -1	-	1	2	3 ^e	-	4	5	6 ^f	ET ^g	
Week	-2 to -1	-	-	1	2	3 ^e	-	4	5	6 ^f	ET ^g	10
Day	-15 to -1	1/ Baseline ^h	4	7±2	14±2	21±2	24	28±2	35±2	42±2	45±2	NA
BACS		X								X	X	
SF-6D		X								X	X	
Safety Assessments												
Physical/neurological examination ⁱ	X										X	X
Limited physical examination ^o		X										
Height (Screening only) and weight	X	X				X					X	X
ECG ^p	X	X		X	X	X		X	X		X	X
Heart rate and blood pressure (including orthostatic) ^q	X	X		X	X	X		X	X		X	X
Respiratory rate and temperature	X	X		X	X	X		X	X		X	X
C-SSRS ^r	X	X		X	X	X		X	X		X	X
EPS (SAS, AIMS, BARS) ^s	X	X				X					X	X
Prior/concomitant treatments ^t	←-----→											
Adverse event monitoring ^u		←-----→										

Trial Periods/Phases	Screening Period ^{a,b,c}	Treatment Period										Follow-up ^d	
		-	-	1	2	3 ^e	-	4	5	6 ^f	ET ^g		
Week	-2 to -1	-	-	1	2	3 ^e	-	4	5	6 ^f	ET ^g	10	
Day	-15 to -1	1/ Baseline ^h	4	7±2	14±2	21±2	24	28±2	35±2	42±2	45±2	NA	73±3
Laboratory													
Blood for safety laboratory sample	X	X				X					X	X	
Urine for safety laboratory	X	X				X					X	X	
Prolactin level ^v		X									X	X	
Serum pregnancy test ^w	X												
Urine pregnancy test ^w		X									X	X	
Urine drug screen ^x	X	X											
Hepatitis B, C, HIV	X												
PK blood sample			X ^y			X ^z					X ^{aa}		
Blood sample for future biospecimen research ^{bb}		X											
Other													
Daily morning dose of IMP			←-----→										

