- p. 12-lead ECG assessments will be performed after the participant has been at rest for approximately 3 minutes. At Screening, the average of 3 consecutive ECGs collected 1 to 2 minutes apart will be used to determine participant eligibility; at Baseline, only 1 reading is required for determination of eligibility. At approximately 2 hours following dosing at weekly time points, single 12-lead ECGs will be obtained. Additional ECGs can be performed at the investigator's discretion (eg, if abnormalities are noted).

- q. At Screening and Baseline, blood pressure and heart rate assessments should be performed in order to confirm eligibility (see Exclusion Criterion in [Section 5.2](#)). Triplicate supine heart rate and blood pressure measurements should be taken at approximately 1-minute intervals predose (Day 1 only, Baseline), and at approximately 2 hours after dosing on Day 1 and Weeks 1 through 6. The triplicate supine heart rate and blood pressure measurements will be followed by a single measurement after approximately 2 minutes in a standing position to allow for orthostatic assessments. Additional time points can be added at the investigator's discretion (eg, if abnormalities are noted). Further details are provided in [Section 8.2.3](#) and in the Operations Manual.
- r. The "Baseline/Screening" C-SSRS form will be completed for all participants at Screening to determine eligibility and the "Since Last Visit" C-SSRS form will be completed at Baseline to ensure that the participant continues to qualify for the trial. The "Since Last Visit" C-SSRS form will also be completed at weekly time points after Baseline.
- s. EPS assessments can be completed at any time during the trial, per investigator discretion, if symptoms are present.
- t. Prior and concomitant medications should be recorded from Screening through the participant's last visit/contact.
- u. Adverse events (serious and nonserious) should be recorded from the first dose of IMP through the participant's last visit/contact.
- v. The Week 6 prolactin results will be partially blinded; the investigator will be notified if the prolactin levels exceed a predefined limit with instructions to send the participant for appropriate follow-up.
- w. For women of childbearing potential only. Pregnancy tests can be performed at any time during the trial at the discretion of the investigator if pregnancy is suspected. Any urine pregnancy tests that are positive must be confirmed using a serum test.

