3 OBJECTIVES AND ENDPOINTS

Table 2 Objectives and Endpoints

Objectives	Endpoints
Primary	
Primary Endpoint:
 
 • Change from Baseline at Week 6 in the PANSS total score 
Key Secondary Endpoint:
 
 • Change from Baseline at Week 6 in the CGI-S score 
Secondary Endpoints:
 
 • Change from Baseline at all time points in PANSS total score • Change from Baseline at all time points in CGI-S score • Percentage of responders at Week 6 (responders defined as $\geq 30\%$ reduction from Baseline in PANSS total score) 
Exploratory Endpoints:
 
 • CGI-I at Weeks 3 and 6 • Change from Baseline at all time points in PANSS positive, negative, and general psychopathology subscale scores • Change from Baseline at all time points in PANSS Marder Factor scores
Secondary	
 • Treatment-emergent adverse events • Clinically significant changes in electrocardiograms, clinical laboratory assessments and metabolic parameters, standard vital sign measurements, and physical and neurological examination results, including body weight • Clinically significant findings in suicidality assessed using the C-SSRS • Extrapyramidal symptoms evaluated using the change from Baseline in SAS, AIMS, and BARS assessments

Objectives	Endpoints
Exploratory	

 To evaluate the plasma pharmacokinetics of emraclidine and its metabolite, CV-0000364, following 2 fixed oral doses (15 mg QD and 30 mg QD) of emraclidine in adult participants with schizophrenia experiencing an acute exacerbation of psychosis 	
 Pharmacokinetic parameters for emraclidine and its metabolite, CV-0000364 (C_{max} and AUC_{tau})

 To evaluate quality of life and cognition following 2 fixed oral doses (15 mg QD and 30 mg QD) of emraclidine in adult participants with schizophrenia experiencing an acute exacerbation of psychosis 	
 Change from Baseline at Week 6 in BACS symbol coding test Change from Baseline at Week 6 in SF-6D

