5.1 Inclusion Criteria

Individuals are eligible for participation in this trial only if all of the following criteria apply:

General	
1.	Male and female participants, ages 18 to 65 years, inclusive, at the time of signing the ICF.
Target Disease Characteristics	
2.	Primary diagnosis of schizophrenia per DSM-5, as confirmed by the MINI for Psychotic Disorders version 7.0.2.
3.	CGI-S ≥ 4 (moderately to severely ill) at the time of signing the ICF and Baseline.

4.	
PANSS Total Score between 85 and 120, inclusive, at the time of signing the ICF and at Baseline.
 
Additionally, participants must meet a score of ≥ 4 (moderate or greater) for ≥ 2 of the following Positive Scale items at the time of signing the ICF and at Baseline:
 
 • Positive Scale Item 1 (delusions) • Positive Scale Item 2 (conceptual disorganization) • Positive Scale Item 3 (hallucinatory behavior) • Positive Scale Item 6 (suspiciousness/persecution)
5.	
Experiencing an acute exacerbation or relapse of psychotic symptoms, with onset less than 60 days prior to signing the ICF.
 
 • Participant requires hospitalization for this acute exacerbation or relapse of symptoms • If participant is already an inpatient at the time of signing the ICF, has been hospitalized for ≤ 14 days for the current episode of psychosis at the time of signing the ICF, excluding hospitalization for psychosocial reasons
6.	
Scores as follows (normal to mild symptoms) at the time of signing the ICF and Baseline (Day 1):
 
 • All individual items of the SAS < 2 • All individual items (Items 1-7) of the AIMS < 2 • Clinical global assessment item of the BARS < 3
7.	
Willing to discontinue all prohibited medications to meet protocol-required washouts prior to and during the trial period.

8.	
Resides in a stable living environment as demonstrated by the ability to provide contact information for themselves and/or family/friend/caregiver.

Other and Administrative Criteria

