## 4.2. Analysis Visit Windows

Data collected longitudinally across visits will be summarized and analyzed by visit.

Assessments made on scheduled visits will be mapped to an appropriate analysis visit that corresponds to the nominal visit. Early termination and unscheduled visits will be assigned to visit windows based on the study day of the event. For unscheduled and early termination vital signs, timepoint will be windowed. For unscheduled and early termination vital signs that occur on study day 1, the time of the last scheduled pre-dose triplicate on Day 1 (nominal visit) will be used to determine if the timepoint should be windowed to a pre-dose or post-dose timepoint. For all other study days, the timepoint will be assumed to be post-dose.

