**Table 2: Analysis Visit Window**

Study Day of Early Termination or Unscheduled Visit	Analysis Visit	Analysis Visit Target Day
PANSS and CGI-S		
$\leq 1$	Baseline	1
2-10	Week 1	7
11-17	Week 2	14
18-24	Week 3	21
25-31	Week 4	28
32-38	Week 5	35
$\geq 39$	Week 6	42
ECGs and C-SSRS		
$\leq 1$ (before Day 1 assessment + 1 hour)	Baseline	1
2-10	Week 1	7
11-17	Week 2	14
18-24	Week 3	21
25-31	Week 4	28
32-40	Week 5	35
$\geq 41$	Week 6	45
Blood Pressure and Heart Rate		
$\leq 1$ (before Day 1, Pre-Dose assessment)	Baseline	1
1 (after Day 1, Pre-Dose assessment)	Day 1	1
2-10	Week 1	7

Study Day of Early Termination or Unscheduled Visit	Analysis Visit	Analysis Visit Target Day
11-17	Week 2	14
18-24	Week 3	21
25-31	Week 4	28
32-40	Week 5	35
≥ 41	Week 6	45
Respiratory Rate and Temperature		
≤ 1 (before Day 1, Pre-Dose assessment)	Baseline	1
2-10	Week 1	7
11-17	Week 2	14
18-24	Week 3	21
25-31	Week 4	28
32-40	Week 5	35
≥ 41	Week 6	45
Extrapyramidal Symptoms (SAS, AIMS, BARS), Laboratory Assessments (Chemistry, Hematology, Urinalysis, and Coagulation) and Weight		
≤ 1	Baseline	1
2 - 32	Week 3	21
≥ 33	Week 6	45
CGI-I		
1 - 32	Week 3	21
≥ 33	Week 6	42
BACS, SF-6D, and Laboratory Assessments (Prolactin and Urine Pregnancy Test)		
≤ 1	Baseline	1
≥ 2	Week 6	45

If assessments are collected multiple times within a given visit window, the scheduled visit, if available, will be used for summary presentations. If no scheduled visit is available, then the result closest to the scheduled visit date will be used for summary presentations. If two unscheduled measurements (early termination or unscheduled visit) have the same distance to the target date, the later value will be used. If a subject has multiple non-missing unscheduled values on the same date, then the last one is used, as determined by the time collected, if available.

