#### **5.15.8. Extrapyramidal Symptoms (EPS)**

The total score of each EPS assessment scale: Simpson-Angus Scale (SAS), Abnormal Involuntary Movement Scale (AIMS), and Barnes Akathisia Rating Scale (BARS), will be listed and summarized by treatment group, and visit, with the corresponding changes from baseline, using descriptive statistics.

An MMRM analysis as described in [Section 5.9.2](#), except Cohen's D, will be used to compare the changes from baseline in the total score of each scale of each dose group with the placebo group.

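### SAP 5.15.8 has no worst post-baseline EPS summary, so symptom-triggered and some early-termination SAS, AIMS and BARS exams are compared between arms only if the scheduled exam is missing

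*Protocol*

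**What the plan says.** **Collection.** The Schedule of Assessments (Protocol 1.3) has EPS scales at Screening, Baseline, Week 3 (Day 21±2), Week 6 (Day 45±2) and ET. Footnote s adds: "EPS assessments can be completed at any time during the trial, per investigator discretion, if symptoms are present".

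**Endpoint.** Protocol section 3 lists under the secondary (safety) objective: "Extrapyramidal symptoms evaluated using the change from Baseline in SAS, AIMS, and BARS assessments".

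**Windows.** SAP 4.2 states: "Early termination and unscheduled visits will be assigned to visit windows based on the study day of the event". The Table 2 block beginning "Extrapyramidal Symptoms (SAS, AIMS, BARS), Laboratory Assessments" has two post-baseline slots, Days 2-32 (Week 3) and Day 33 onward (Week 6).

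**Record selection.** The text under Table 2 reads: "If assessments are collected multiple times within a given visit window, the scheduled visit, if available, will be used for summary presentations". If there is no scheduled record, the one closest to the scheduled date is taken.

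**Analysis.** Under SAP 5.15.8 the total score of each scale "will be listed and summarized by treatment group, and visit, with the corresponding changes from baseline, using descriptive statistics". An MMRM of change in total score follows. The section shows no redaction and contains no maximum, worst-case or any-time summary.

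**Entry limits.** Inclusion criterion 6 requires at consent and Baseline "All individual items of the SAS < 2", with AIMS items 1-7 also below 2 and the BARS global item below 3.

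**The concern.** Footnote s exists so that EPS arising between two widely spaced exams can be rated when it is present. The window and selection rules then set that rating aside in favour of a scheduled exam that may have been done weeks earlier or later, when the participant had no symptoms. The same happens to an ET exam up to Day 32 in someone who has already had the Week 3 exam, so EPS rated at withdrawal can drop out of the summaries too.

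Elsewhere the SAP does not rely on by-visit summaries alone. It plans shifts to the worst laboratory grade (5.15.3), the highest weight increase (5.15.4.2), any post-baseline QTcF occurrence (5.15.5) and the maximum C-SSRS result (5.15.7). EPS has only two scheduled looks on treatment, against weekly C-SSRS, and has no such summary. No reason is given.

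What is at stake is part of a named safety endpoint. The protocol's background presents EPS as a limiting toxicity of older antipsychotics (2.2.1), and it cites the absence of relevant change on EPS scales as prior safety evidence (2.2.3). A reader would want to know whether any arm had more participants reaching a clear scale rating at any time on treatment. The planned outputs do not answer that.

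**Working it through.** The plan states no figure on this point, so there is none to reproduce. The check has two parts.

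**1. What happens to each type of EPS record**

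| Record | Window | Scheduled exam in that window? | Used in summaries and MMRM? |
|---|---|---|---|
| Triggered, Days 2-32 | Week 3 | yes | no, listing only |
| Triggered, Day 33 on | Week 6 | yes | no, listing only |
| ET up to Day 32, after a completed Week 3 exam | Week 3 | yes | no, listing only |
| ET before the Week 3 exam | Week 3 | no | yes, if closest to target |
| ET from Day 33 | Week 6 | no | yes, if closest to target |
| Triggered, scheduled exam missing | either | no | yes, if closest to target |

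**2. How often the two scheduled exams would miss an episode**

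Inputs from the documents: a 45-day treatment period, with exams on Days 21 and 45 (each ±2).

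Assumptions, because the documents give no EPS duration or onset: one episode of d whole days, onset equally likely on each of Days 1-45, participant still on treatment, and each exam rating the current state only.

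An episode overlaps Day 21 for d of the 45 possible onset days and overlaps Day 45 for another d. For d up to 24 no onset day is counted twice. Hence:

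share seen = 2d/45; share missed = 1 − 2d/45.

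| d (days) | seen | missed |
|---|---|---|
| 3 | 6/45 = 13% | 87% |
| 5 | 10/45 = 22% | 78% |
| 7 | 14/45 = 31% | 69% |
| 10 | 20/45 = 44% | 56% |
| 11 | 22/45 = 49% | 51% |
| 12 | 24/45 = 53% | 47% |
| 14 | 28/45 = 62% | 38% |
| 21 | 42/45 = 93% | 7% |

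Under these assumptions a majority is missed up to 11 days and a minority from 12 days.

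**Sensitivity**

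- Both exams moved 2 days earlier or later: 7-day episodes missed 69% to 73%.
- Onset uniform over Days 1-28: missed 89% (3 days), 75% (7), 64% (10), 50% (14).
- Onset uniform over Days 1-14: missed 100% (3 days), 100% (7), 79% (10), 50% (14).

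These are the shares for which a triggered exam, if one was done, would be the only scale rating of the episode. The calculation does not model how often investigators perform triggered exams; the documents give no expected frequency.

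**The case against.** The strongest reply is that the endpoint is delivered as defined. It is change from Baseline on three scales. Protocol 9.3.5 promises only descriptive statistics for EPS, and the SAP adds an MMRM. Preferring the scheduled record is sound for a by-visit mean, because feeding in exams done when symptoms are present would make sampling depend on the outcome. No passage promises a worst-case EPS summary. All of this stands, and it is why the MMRM should be left alone.

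Four stronger readings are tempting, and the documents do not support them.

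- *Most EPS episodes are lost.* This depends on assumed duration and onset. Dosing is fixed, dose modification is not permitted (6.5), and anticholinergics and beta-receptor antagonists are prohibited during treatment (Table 5), so short episodes cannot be presumed.
- *The analysis is biased toward no difference from placebo.* The Week 3 and Week 6 means are not biased for what they estimate. They simply do not describe the time between.
- *Low baseline scores hide worsening.* A floor limits improvement and leaves room to worsen. Ten SAS items each below 2 also allow a total of up to 10 out of 40.
- *Triggered exams are never used, or these episodes go unreported.* They are used when the scheduled exam is missing. EPS recorded as adverse events enters the TEAE tables (5.15.1). That section has redactions, so an EPS event grouping cannot be excluded. TEAE tables still do not use the scale ratings.

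The comparison with other domains also has limits. Weight is taken across visits without expressly including unscheduled records, and supine blood pressure and heart rate use selected or averaged records. There is no uniform all-records rule, but EPS still lacks any worst-value summary.

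**Conclusion.** The gap is real but narrow. When the scheduled exam in a window exists, triggered exams, and ET exams up to Day 32 after a completed Week 3 exam, do not enter any comparison between arms on SAS, AIMS or BARS. The by-visit MMRM remains valid for Weeks 3 and 6, and between-visit EPS is compared only through TEAEs.

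Under uniform onset over Days 1-45, the two exams miss about 87% of 3-day, 69% of 7-day, 56% of 10-day and 38% of 14-day episodes. A majority is missed only up to about 11 days. Duration and onset are assumptions, and earlier onset raises the missed share.

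This is a cheap improvement to a secondary safety endpoint. It is not a contradiction in the plan, and no primary or key secondary inference is affected.

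**What to change.** Keep the by-visit summaries and MMRM in SAP 5.15.8 unchanged. Add one supportive table on the safety set:

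- **Categorical.** Number and percentage per arm, with difference from placebo and 95% CI, of participants whose maximum post-baseline value over all records (scheduled, unscheduled, ET) reaches any SAS item ≥2, any AIMS item 1-7 ≥2, or BARS global item ≥3. Restrict it to participants below those limits at Baseline, so that eligibility deviations do not count as new EPS.
- **Continuous.** Worst post-baseline change in each scale's total score, by arm. SAP 3.2.9.2 does not define a BARS total, so state the one used.

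Label the table descriptive. State that the cut-offs are the protocol's entry limits, borrowed rather than validated as event definitions, and that triggered exams are done at blinded investigators' discretion.

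The cost is SAP wording and one table from data already collected, with no protocol change. The downside is uneven use of triggered exams between sites; with sites and raters blinded (Protocol 6.3.2), this should not favour an arm.

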2 INTRODUCTION

2.1 Trial Rationale

Emraclidine (previously referred to as CVL-231) is a brain penetrant mAChR activator that selectively binds to the M4 muscarinic receptor subtype while sparing other muscarinic receptor subtypes (M1, M2, M3, and M5). Emraclidine is being developed for treatment of psychosis in schizophrenia.

The aim of this trial is to investigate the efficacy, safety, and tolerability of 2 fixed doses of emraclidine (15 mg QD and 30 mg QD) in participants with schizophrenia who are experiencing an acute exacerbation of psychosis.

2.2 Background

2.2.1 Disease Overview

Schizophrenia is characterized by positive symptoms (eg, hallucinations and delusions), negative symptoms (eg, emotional blunting and lack of motivation), and deficits in cognitive function (eg, attention, information processing, and working memory) (Shekhar et al, 2008). Treatment of schizophrenia is currently limited to typical and atypical antipsychotic medications that act by blocking various dopamine (D1 and D2) receptors in the brain (Shekhar et al, 2008; Howes and Kapur, 2009). However, these antipsychotics typically also bind to a number of additional receptor subtypes, including other dopaminergic, serotonergic, muscarinic, adrenergic, and histaminergic receptor subtypes (Miron et al, 2014).

The first-generation antipsychotics (eg, chlorpromazine, haloperidol, and fluphenazine) are effective at controlling some symptoms of schizophrenia, especially positive symptoms such as delusions and hallucinations, due to a combination of D2 blockade and anticholinergic and antihistaminergic effects (Buoli et al, 2016; Altamura et al, 2011). However, the use of these first-generation antipsychotics is limited by severe antidopaminergic side effect such as EPS, tardive dyskinesia, and hyperprolactinemia (Schneider et al, 2006; Huybrechts et al, 2012; Foster et al, 2016).

The “atypical” antipsychotics, of which clozapine was the prototype, have reduced extrapyramidal side effects yet retain antipsychotic potency, likely due to a more rapid dissociation from D2 receptors combined with potent serotonergic (5HT2A) blockade (Kapur and Seeman, 2000; Kapur and Seeman, 2001; Solmi et al, 2017). However, these atypical antipsychotics are associated with off-target receptor mediated metabolic effects and weight gain (Nasrallah, 2008).

Recent literature suggests that for xanomeline, an M1/M4 preferring mAChR agonist, its antipsychotic efficacy may be driven primarily by M4 mAChR stimulation (Woolley et al, 2009; Byun et al, 2014; Brannan et al, 2021), and that a selective M4 mAChR activator could convey similar clinical benefits. Presynaptic expression of the

M4 mAChR on cholinergic interneurons regulates striatal acetylcholine and dopamine equilibrium, the imbalance of which is hypothesized to contribute to the symptoms of psychosis observed in schizophrenia. ([Howes and Kapur, 2009](#)).

2.2.2 Nonclinical Experience

Emraclidine is a novel, brain penetrant, orally bioavailable, small molecule, reversible activator of M4 mAChR. Presynaptic expression of the M4 mAChR on cholinergic interneurons regulates striatal acetylcholine and dopamine equilibrium, the imbalance of which is hypothesized to contribute to psychosis in schizophrenia ([Howes and Kapur, 2009](#)).

Nonadverse treatment-related increases in blood pressure and heart rate, decreases in PR interval and/or RR interval, and shortening of the QT interval (without changes in QTc) were observed in single-dose nonpivotal and pivotal dog cardiovascular safety pharmacology studies with resolution of these findings by 9 hours postdose. In the pivotal 1- and 3-month repeat-dose toxicity studies, similar effects were observed (ie, increased heart rate and decreased PR, RR, and/or QT interval [without changes in QTc]). In the 3-month dog study, the greatest (magnitude) increase in heart rate was observed on Day 1 in the mid- and high-dose groups (≥ 3.75 mg/kg/day) and was considered adverse based on the magnitude of increase. By Days 43 and 91, heart rate was still increased in these dose groups compared with control animals, but the differences were of small magnitude, and all mean heart rate values were within the normal range for dogs. The reduced magnitude of heart rate increase on Days 43 and 91 are indicative and consistent with the development of tolerance to the emraclidine effects on heart rate. With the exception of Day 1 in the 3-month study, these heart rate increases in the pivotal 1- and 3-month dog toxicity studies were considered nonadverse as there were no corresponding adverse in-life or postmortem findings, including histopathological effects on cardiovascular tissues. Similarly, in the 9-month repeat-dose dog toxicity study, adverse (based on magnitude of increase) heart rates were generally observed at the start of the study (Day 1 for the high dose group and Days 8 and 15 during dose-escalation) and appeared to attenuate as the study progressed (reduced magnitude of heart rate increase generally by Day 22 in previously affected groups). There were no corresponding adverse in-life or postmortem findings, including histopathological effects on cardiovascular tissues. Overall, the cardiovascular effects that were noted in all studies were monitorable, reversible, and not associated with cardiac or vascular pathologies.

The nonclinical safety profile of emraclidine and CV-0000364 metabolite have been adequately characterized to support clinical trials of up to 13 weeks in duration in women of childbearing potential and men with use of highly effective contraception for the duration of systemic exposure.

Please refer to the emraclidine Investigator's Brochure for more detailed information.

2.2.3 ***Clinical Experience***

Safety, tolerability, and PK of emraclidine were evaluated following single doses in healthy participants (Trial C2561001) and following multiple ascending doses in participants with schizophrenia (Trial CVL-231-SCH-001).

In Trial C2561001, emraclidine single oral doses in the range of 0.3 mg to 30 mg were administered under fasted conditions. There were transient changes in heart rate and blood pressure that appeared to be dose related and were most prominent at the 30 mg dose level. These changes returned toward baseline by 24 hours. Two AEs of moderate severity associated with cardiovascular assessments (orthostatic hypotension and sinus tachycardia) were observed at the 30 mg dose level.

In the Phase 1b, 2-part, multiple ascending dose trial in participants with schizophrenia (Trial CVL-231-SCH-001), 39 participants with stable schizophrenia received multiple doses of emraclidine of 5, 10, 20, or 30 mg QD for up to 14 days or 20 mg BID for up to 28 days (7-day titration; 21 days target dose) during Part A. An additional 54 participants with acute exacerbation of psychosis received treatment with emraclidine 30 mg QD (27 participants) or 20 mg BID (27 participants) for up to 42 days in Part B of the trial.

In contrast with healthy participants, the effect of emraclidine on blood pressure in participants with schizophrenia was variable, nonsustained, and had no clear dose relationship. In Part A of Trial CVL-231-SCH-001, emraclidine at doses \geq 20 mg QD appeared to be associated with modest, transient increases in both systolic and diastolic blood pressure; none of these increases were associated with TEAEs. emraclidine was also associated with an increase in heart rate that appeared to be dose dependent and persisted throughout the Treatment Period. There were no TEAEs of tachycardia. In Part B of the trial, modest elevations in systolic and diastolic blood pressure and heart rate were observed with emraclidine compared with placebo early in the Treatment Period; these elevations decreased over time. The average change from Baseline during Week 6 in systolic and diastolic blood pressure and heart rate for both the emraclidine 30 mg QD and 20 mg BID groups showing no clinically meaningful difference versus placebo. The average change for the emraclidine 30 mg QD group versus placebo at the 2-hour post morning dose time point during Week 6 were +1.2 mmHg, -0.1 mmHg, and +4.4 bpm for systolic blood pressure, diastolic blood pressure, and heart rate, respectively.

Emraclidine was safe and generally well tolerated in participants with schizophrenia. The most frequently reported TEAEs in emraclidine treated participants (>5% of emraclidine participants) in Part A were headache (4/39 participants; 10%), dizziness (2/39; 5%), insomnia (2/39; 5%), and increased weight (2/39; 5%) and in Part B were headache (15/54; 28%), nausea (4/54; 7%), and back pain, blood creatinine phosphokinase increased, dizziness, dry mouth, increased weight, and somnolence (3/54; 6% each). No clinically meaningful changes were observed in ECGs, except increase in heart rate consistent with vital sign findings. No clinically relevant changes were observed in clinical laboratory findings, or clinical scales for extrapyramidal symptoms or suicidality.

The PK of emraclidine were characterized by rapid absorption and biphasic elimination, with the median T_{max} ranging from 1.0 to 1.8 hours under fasted conditions (3.0 hours in the fed state) and the mean $t_{1/2}$ ranging between 9.4 hours and 12.2 hours across following single doses in healthy participants. Increase in emraclidine C_{max} and AUC appeared to be dose proportional. The results of a pilot food effect trial at the 10 mg dose suggest that administration of the compound immediately following a high-fat diet result in a slight reduction in C_{max} without significantly affecting the overall bioavailability of emraclidine. Pharmacokinetic data from Trial CVL-231-SCH-001 suggest that PK of emraclidine in participants with schizophrenia is similar to that observed in healthy participants. The increase in C_{max} values for emraclidine was roughly dose proportional. However, the high interparticipant variability in emraclidine AUC values, similar to results from the single ascending dose trial, affected accurate dose proportionality assessment.

Both the emraclidine 30 mg QD and the 20 mg BID doses demonstrated clinically meaningful antipsychotic activity compared with placebo in Part B of Trial CVL-231-SCH-001. The emraclidine 30 mg QD dose resulted in a statistically significant and clinically meaningful mean reduction from Baseline of 19.5 points in the PANSS total score (12.7-point difference from placebo group; nominal $p=0.023$) at Week 6. The emraclidine 20 mg BID dose resulted in a statistically significant and clinically meaningful mean reduction from Baseline of 17.9 points in PANSS total score (11.1-point difference from placebo group; nominal $p=0.047$) at Week 6. These results were further supported by clinically meaningful improvements versus placebo on the PANSS positive, negative, and general psychopathology subscale scores, as well as on the CGI-S scale score.

Please refer to the emraclidine Investigator's Brochure for more detailed information.

